## 5.2 Secondary Objectives:

### 5.2.1 Engraftment in patients with non-malignant diseases (Stratum A):

- a. Engraftment will be defined as the development of an ANC >500 for 3 consecutive days plus donor CD14/15 cells >70%.
- b. The historic control for Stratum A will be as follows:

Patients	# of High-Risk Patients	Engraftment	Overall Survival
Enrolled on BU-FLU-rATG 	5	2	4
Enrolled on BU-FLU-C 	5	2	2
Treated with BU off study (2005-10)	5	3	5
Summary	15	6	11

- c. Therefore, the engraftment rate in this population was only 40%. If the observed engraftment rate of this trial is as large as 83% (10/12), we would need a minimum of 12 patients in Stratum A to show a significant improvement ( $\alpha < 0.05$ ) in engraftment rate compared to historic controls at the 5% level.
- d. If 3 patients in Stratum A experience graft rejection, we will close this stratum early for failing to achieve superior engraftment compared to standard-of-care.

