### 1.2.2 Secondary Objectives:

a. To determine if the addition of Clofarabine to a conditioning backbone of Busulfan plus Fludarabine improves the engraftment rate of patients with non-malignant diseases (Stratum A) undergoing allogeneic HCT as compared to historic controls.

b. To determine if the addition of Clofarabine to a conditioning backbone of Busulfan plus Fludarabine improves the full donor chimerism of patients with high-risk myeloid malignancies (Stratum B) undergoing allogeneic HCT as compared to historic controls.

c. To evaluate the pharmacokinetics (PK) of Clofarabine and Fludarabine in a combination nucleoside analogue preparative regimen and define exposure-response relationships with clinical outcomes.

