### 5.2.2 Mixed-Chimerism in patients with high-risk myeloid malignancies (Stratum B):

- a. Full-donor chimerism will be defined by as  $\geq 99\%$  donor cells by STR analysis in all cell lines (CD3, CD14/15, and CD19) in peripheral blood.
- b. The historic control for Stratum B will be the 20 patients who were transplanted from 2005 – 2010 with BU-based regimens and who retrospectively would have been eligible for the current trial. Of these 20 patients, at 100 days post-HCT, only 8 (40%) patients had full-donor chimerism ([name], unpublished data).
- c. If the observed cumulative incidence of full-donor chimerism at Day 100 is at least 79%, we will need a minimum of 19 patients in Stratum B to show a

significant improvement (alpha < 0.05) in incidence of full donor chimerism compared to historic controls at the 5% level.

d. If 5 patients in Stratum B experienced mixed-donor chimerism at Day 100, we will close this stratum early for failing to achieve superior donor cell engraftment compared to standard-of-care.

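### The Stratum A historic-control rows add to 7 of 15 engrafted (46.7%), but the plan uses 6 of 15 (40%) to set its 10/12 threshold and 12 patients

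*Combined protocol and SAP*

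**What the plan says.** Section 1.2.2(a) makes it a secondary objective to determine whether adding clofarabine "improves the engraftment rate of patients with non-malignant diseases (Stratum A) undergoing allogeneic HCT as compared to historic controls". Section 5.2.1(a) gives the endpoint: "Engraftment will be defined as the development of an ANC >500 for 3 consecutive days plus donor CD14/15 cells >70" per cent.

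The control table in section 5.2.1(b) reads:

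| Source of controls | High-risk patients | Engrafted | Alive |
|---|---|---|---|
| BU-FLU-rATG trial | 5 | 2 | 4 |
| BU-FLU-C trial | 5 | 2 | 2 |
| Busulfan off study, 2005-10 | 5 | 3 | 5 |
| Summary | 15 | 6 | 11 |

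Section 5.2.1(c) continues: "Therefore, the engraftment rate in this population was only 40" per cent. It then states: "If the observed engraftment rate of this trial is as large as 83% (10/12), we would need a minimum of 12 patients" to show a significant improvement at the 5% level. No test or sidedness is given. Section 5.2.1(d) adds: "If 3 patients in Stratum A experience graft rejection, we will close this stratum early". Section 5.3(a) carries the 12 patients into the total of 31.

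**The concern.** The engraftment rows and their own total cannot both be right. The 40% in the text is only the Summary entry expressed as a percentage, so it does not independently support the 6. The comparison is a stated objective, and both its threshold and its patient number are argued from that rate.

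If the rows are right, 10 of 12 could be reported as a significant improvement when it is not one by a Fisher test, the family that best fits the plan's figures. If nothing is corrected beforehand, the analyst has to choose between 6 and 7, and choose a test, possibly with the results in view. At exactly 10/12 those choices can decide the conclusion.

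**Working it through.** **Inputs.** Control rows, Summary, 10/12, minimum of 12 and the 5% level: section 5.2.1. Planned 12 patients: section 5.3(a). Stratum B figures, used only to probe the unnamed test: section 5.2.2.

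**Step 1: column sums.**
- Patients: 5 + 5 + 5 = 15 (printed 15).
- Alive: 4 + 2 + 5 = 11 (printed 11).
- Engrafted: 2 + 2 + 3 = 7 (printed 6).
- Rates: 6/15 = 40.0%; 7/15 = 46.7%. The gap to 10/12 (83.3%) is 43.3 or 36.7 percentage points.

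**Step 2: reproduce the plan's figure with 6/15.** For Fisher's exact test with M engrafted among all 27 patients, P(X = j) = C(12, j) × C(15, M − j) / C(27, M). The two-sided p-value adds every table no more probable than the one observed.

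For 10/12 against 6/15, M = 16 and C(27,16) = 13,037,895.
- Upper tail, j = 10 to 12: 330,330 + 36,036 + 1,365 = 367,731, so one-sided p = 0.028.
- Lower tail, tables no more probable than j = 10 (j = 1 to 4): 12 + 990 + 23,100 + 225,225 = 249,327.
- Two-sided p = 617,058 / 13,037,895 = 0.047.

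The neighbouring results are not significant: 9/12 gives 0.121 and 9/11 gives 0.0506. Two-sided Fisher therefore reproduces both the 10/12 threshold and the minimum of 12.

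**Step 3: repeat with 7/15.** M = 17 and C(27,17) = 8,436,285.
- Upper tail: 424,710 + 60,060 + 3,003 = 487,773, so one-sided p = 0.058.
- Lower tail (j = 2 to 5): 66 + 3,300 + 51,975 + 360,360 = 415,701.
- Two-sided p = 903,474 / 8,436,285 = 0.107.

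For 11/12 against 7/15, M = 18 and C(27,18) = 4,686,825. The tails are 77,220 + 5,005 and 220 + 7,425, so p = 89,870 / 4,686,825 = 0.019.

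**Step 4: dependence on the test, for 10/12.**

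| Test | p against 6/15 | p against 7/15 |
|---|---|---|
| Fisher, two-sided | 0.047 | 0.107 |
| Fisher, one-sided | 0.028 | 0.058 |
| Chi-square, uncorrected | 0.023 | 0.0499 |
| Chi-square, Yates | 0.060 | 0.119 |
| One-sample binomial at the fixed rate, two-sided | 0.005 | 0.017 |

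Only the two Fisher versions cross 0.05 because of the one-patient difference. Yates is above 0.05 either way; the other two stay below it.

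**Step 5: can the test be inferred?** The first significant sample size, with an observed rate no higher than 10/12, is:

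| Test | Against 6/15 | Against 7/15 |
|---|---|---|
| Fisher, two-sided | 12 | 22 (18/22, p = 0.036) |
| Fisher, one-sided | 11 | 17 |
| Chi-square, uncorrected | 10 | 12 |
| Chi-square, Yates | 16 | 23 |

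The plan's 12 matches two-sided Fisher with 6/15, but also uncorrected chi-square with 7/15. The stated figures therefore do not settle which count is right.

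Stratum B has a control of 8/20 ("Of these 20 patients, at 100 days post-HCT, only 8 (40%) patients had full-donor chimerism"). Two-sided Fisher gives 14/19 p = 0.054 and 15/19 p = 0.022, in line with the 79% threshold and closure at 5. It does not give the stated minimum ("If the observed cumulative incidence of full-donor chimerism at Day 100 is at least 79%, we will need a minimum of 19 patients"), because 11/14 is already significant (p = 0.038). None of the four two-sample tests gives 19. Two-sided Fisher is the best fit, not an established choice.

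**Step 6: closure rule.** This step assumes that each rejection counts as an endpoint failure, that the test is two-sided Fisher and that the control is 7/15. Three failures leave at most 9/12 (p = 0.239), so closing then would not stop a stratum that could still succeed. Two failures already leave at most 10/12 (p = 0.107), so the stratum would continue although 11/12 was out of reach.

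**The case against.** The mismatch itself cannot be defended away. A misread table is unlikely: every cell is present, the 40% in the text confirms a printed total of 6, and nothing suggests that a row digit was misread. No other section gives a second Stratum A engraftment count.

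The stronger objection concerns consequence. The loss of significance needs both that the rows are right and that a Fisher-type test is used, and the documents establish neither. If one row is overstated by one, nothing in the design changes. The comparison is non-randomised, against 15 retrospective patients, and is a secondary objective in one stratum of a study that section 9.2 calls a pilot. The toxicity justification for 31 patients in section 5.1(c) does not use this count. All of this stands and limits the reach of the point.

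The link to the closure rule is also an inference. Section 5.2.1(d) gives no derivation and does not equate rejection with failing the definition in 5.2.1(a). What is supported is that the rule must be reconciled with the threshold if the count changes.

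None of this removes the need to act. A stated objective has a comparator that contradicts itself, and the reader cannot tell which value is true.

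**Conclusion.** The concern holds: the section is wrong as written. What is certain is a one-patient contradiction in the control count, 40.0% against 46.7%, in the figure on which the plan rests the Stratum A threshold and patient number. Which entry is wrong is unknown.

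If 7/15 is right and two-sided Fisher is the test, 10/12 is not significant and 11/12 is required. Under uncorrected chi-square 10/12 would pass by less than 0.0001, and under the one-sample test it would pass clearly, though that test treats a rate from 15 patients as known. If 6/15 is right, the stated threshold and minimum stand under two-sided Fisher. The contradiction must be resolved before the comparison is analysed.

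**What to change.** 1. Check the 15 historical records against the definition in section 5.2.1(a) and correct whichever entry is wrong, row or Summary.
2. Name the test and its sidedness in section 5.2.1(c) before analysis. Two-sided Fisher at 5% agrees with the existing 10/12 and 15/19 thresholds.
3. If 7/15 is confirmed, restate the control rate as 46.7%. Under two-sided Fisher with 12 patients, restate the threshold as 11/12 and remove the claim that 12 patients suffice at an observed 83%. Reconcile section 5.2.1(d) with the corrected threshold; whether and when to close the stratum is for the sponsor to decide.
4. If a row is wrong, correct the row; the threshold and the 12 patients then stand.

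The cost is a check of 15 records and a wording amendment. Correcting the table does not in itself require more patients. If 7/15 is confirmed, keeping 12 patients means a less favourable threshold, 91.7% instead of 83.3%. Keeping success at about 83% would take a larger stratum under two-sided Fisher: 22 patients if the observed rate may not exceed 10/12, or 19 if it is rounded to the nearest whole patient (16/19, p = 0.030). That choice is the sponsor's.

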### 5.2.2 Mixed-Chimerism in patients with high-risk myeloid malignancies (Stratum B):

- a. Full-donor chimerism will be defined by as  $\geq 99\%$  donor cells by STR analysis in all cell lines (CD3, CD14/15, and CD19) in peripheral blood.
- b. The historic control for Stratum B will be the 20 patients who were transplanted from 2005 – 2010 with BU-based regimens and who retrospectively would have been eligible for the current trial. Of these 20 patients, at 100 days post-HCT, only 8 (40%) patients had full-donor chimerism ([name], unpublished data).
- c. If the observed cumulative incidence of full-donor chimerism at Day 100 is at least 79%, we will need a minimum of 19 patients in Stratum B to show a

significant improvement (alpha < 0.05) in incidence of full donor chimerism compared to historic controls at the 5% level.

d. If 5 patients in Stratum B experienced mixed-donor chimerism at Day 100, we will close this stratum early for failing to achieve superior donor cell engraftment compared to standard-of-care.

#### 5.2.3 Fludarabine and Clofarabine PK

Fludarabine and clofarabine drug levels and potential covariates influencing drug exposure such as renal function and genetic variants involved in drug metabolism, distribution, and activation will be analyzed using standard population pharmacokinetic methods using non-linear mixed effects modeling (NONMEM) software.

#### 5.3 Sample Size:

a. We will plan to accrue 12 patients to Stratum A and 19 patients to Stratum B, for a total of 31 patients.

b. Feasibility: From 2005 to 2010, we transplanted 15 patients that would have met the criteria for enrollment in Stratum A, and 22 patients that would have met the criteria for Stratum B. Presuming at least 90% participation of future patients, this trial should be able to accrue in approximately 6 years if referrals for transplant stay constant, or faster if they increase.

#### 6.0 Risks, Benefits, and Alternatives:

6.1 Risks: Risks and side effects seen with standard-dose Clofarabine are listed on the following table. Side-effects reported in four trials of Clofarabine use during the conditioning regimen prior to HCT are listed first and are **bolded**.

Likely	Less Likely	Rare But Serious
Nausea and/or vomiting	Inflammation and/or sores in the mouth that may make swallowing difficult and are painful (painful mouth sores)	Inflammation or damage to the liver which can be severe and life-threatening and which may lead to an enlarged liver and spleen, bleeding from the veins in the esophagus (the passage that leads from the throat to the stomach), a yellow appearance to the skin and fluid collection in the abdomen which makes it look larger
Diarrhea	Increased levels of a chemical (creatinine) in the blood which could mean kidney damage	Severe loss of water from the body (dehydration) which if untreated may cause low blood pressure and severe loss of salts such as sodium and potassium from the body and could lead to the kidneys failing which could be life-threatening

Elevation in the blood of certain enzymes found in the liver and bilirubin (a substance that comes from the liver breaking down waste products) which may mean the liver is not working as well as normal	The skin and the whites of the eyes appears yellow as a result of too much bilirubin (a substance that comes from the liver breaking down waste products) in the blood	Capillary leak syndrome: a condition in which fluid and proteins leak out of tiny blood vessels and flow into surrounding tissues, resulting in dangerously low blood pressure. Capillary leak syndrome may lead to multiple organ failure such as kidney, heart or liver failure and shock
Fever	Severe rash with redness and pain on the palms of the hand and soles of the feet (Hand-Foot Syndrome)	Inflammation of the pancreas (an organ in the abdomen which produces insulin and certain digestive chemicals) which may affect the function of the pancreas and which may cause pain in the abdomen (belly) which can be severe and may increase the blood sugar
Skin rash	Numbness and tingling in the fingers and toes	Severe inflammation and damage to the large intestine wall which can be life threatening
A fast heartbeat which may cause pain in the chest	Rash with redness or red bumpy rash	Abnormal clotting of the blood that can lead to formation of blood clots and/or bleeding with abnormal findings on neurologic exam
A feeling of extreme tiredness not relieved by sleep	The rapid death of large numbers of tumor cells which can cause the potassium and phosphate salts and the uric acid in the blood to rise quickly and this could lead to a life-threatening irregular heart beat or damage to the kidneys	Severe rashes which can result in loss of skin and damage to mucous membranes and which may be life-threatening (occurred in combination of other drugs known to cause this effect)
A decrease in blood pressure	Fluid build-up in the tissues	Severe kidney damage (which may be permanent)
Pain in the abdomen (belly)	Sleepiness and weakness	Failure of the bone marrow to produce blood cells and platelets which can be life threatening
Fever with a low white blood cell count which could mean that you have an infection and might require hospitalization and treatment with antibiotics	Changes to your emotions such that you feel depressed, anxious, agitated, irritable or confused	A change to the heart such that it does not pump the blood as well which may make you tired, weak, feel short of breath, and retain fluid
Chills	Shaking chills	

Anxiety	High blood pressure	
Loss of appetite	Cough or shortness of breath	
Headache	Reddening of the face with feelings of warmth when the drug is infusing	
Skin rash with inflammation	A fast rate of respiration that may cause pain in the chest	
Itching	Allergic reaction	
Red spots on the skin from low platelets	A change in alertness, concentration, and memory	
Bloody nose	Constipation	

Fewer white blood cells, red blood cells and platelets in the blood (may be prolonged)
 
A low number of white blood cells can make it easier to get infections
 
A low number of red blood cells can make you feel tired and weak
 
A low number of platelets causes you to bruise and bleed more easily
	
A life-threatening form of severe blood infection that usually results from the presence of bacteria and their toxins in the bloodstream and is characterized especially by persistent hypotension with reduced blood flow to organs and tissues and often organ dysfunction
	
Abnormal levels of potassium or magnesium in the body which may require that you take extra potassium by mouth or vein	Tremor (shakiness usually of the hands)	
An increase in an enzyme (called lipase) that helps break down fats in the body	Difficulty sleeping or falling Asleep	
	Fainting	
	Low levels of oxygen in the blood which may make you feel short of breath	
	Pain including back, bone, arm, or leg pain	
	Weight loss	
	Aches and pains in the muscles and joints	
	Bleeding from the bladder, gut, mouth, or gums	
	Vomiting or coughing blood	
	Fluid build-up in the lungs that can make you feel short of breath	
	A life threatening condition in which the level of oxygen in the blood becomes too low or the level of carbon dioxide in the blood becomes too high	
	Damage to the sac around the heart which can lead a build-up of fluid around the heart which may be painful	

	and affect the ability of the heart to work normally but in most cases is only mild and temporary	
	Bruising of the skin from low Platelets	
	Occasional sudden sharp pain in the rectal area	
	Infections including those caused by bacteria, virus, and fungus and can be found in the lung, the blood, the skin and other places in the body	
	Dizziness	
	Abnormal high level of potassium in the blood which may cause irregular heart beat and require drug treatment to lower the level	
	An increase in an enzyme (called amylase) that helps break down starch and sugars in the body	
	A problem in nerve function that may cause pain, numbness, tingling, and muscle weakness in various parts of the body and may affect the ability to perform tasks that require fine movements	

## 6.2 Benefits:

- a. There is a possible benefit to the patient in that the addition of low-dose Clofarabine may decrease the risk of either graft rejection or relapse. If that occurs, then there would likely be a survival benefit to the patient as well.
- b. The characterization of Clofarabine PK and knowledge of associations between drug exposure and outcomes will facilitate the development of individualized dosing strategies for use in pediatric HCT. We expect individualized dosing strategies will lead to improved rates of stem cell engraftment and reduced treatment-related mortality and thus will be a potential future benefit to the segment of society in need of receiving these agents.

## 6.3 Alternatives:

The UCSF standard of care for patients eligible for enrollment on this study would be to receive Busulfan and Fludarabine, without the addition of Clofarabine, for the pre-HCT conditioning regimen.

## 7.0 Subject Recruitment and Consent Process

### 7.1 Subject Recruitment

a. Source: Subjects are referred from outside physicians and immunology and hematology clinics and specialists.

b. Initial contact: Usually, patients and parents are initially seen in the pediatric BMT outpatient clinic. Occasionally, the initial contact is as an inpatient.

## 7.2

### Consent Process:

There is an initial consultation evaluation in the BMT outpatient clinic for all prospective patients and their parents at which the basic concepts of transplantation are reviewed including the overall risks and benefits of the procedure, the donor search, and the main aspects of the transplant, i.e., the estimated length of hospital stay, administration of chemotherapy, and the major side effects and complications, both acute and long term. When it is apparent that a donor is available, a second outpatient meeting occurs with the family, and the protocol is discussed in more detail including who the likely donor will be (if known based upon HLA typing). This is generally within 2-3 weeks of the potential admission to the BMT unit. If the parents want to proceed, the evaluations are done on the patient and donor. Once this is complete and at least 3 days prior to admission to the BMT unit, a final informed consent conference is held to review the results of the work-up and to obtain final signed agreement. At that meeting, the attending discusses the donation procedure with the donor (if related).

All participants must be provided a consent form describing the study with sufficient information for participants to make an informed decision regarding their participation. Participants must sign the IRB-approved informed consent form prior to participation in any study specific procedure. The participant must receive a copy of the signed and dated consent document. The original signed copy of the consent document must be retained in the medical record or research file.

## 8.0 Reporting and Documentation of Adverse Events

### 8.1 Definitions of Adverse Events

#### 8.1.1 Adverse Event

An adverse event (also known as an adverse experience) is defined as any untoward medical occurrence associated with the use of a drug in humans, whether or not considered drug related. More specifically, an adverse event (can be any unfavorable and unintended sign (e.g., an abnormal laboratory finding), symptom, or disease temporally associated with the use of a drug, without any judgment about causality. An adverse event can arise from any use of the drug (e.g., off-label use, use in combination with another drug) and from any route of administration, formulation, or dose, including an overdose.

#### 8.1.2 Adverse reaction

An adverse reaction is defined as any adverse event caused by the use of a drug. Adverse reactions are a subset of all suspected adverse reactions for which there is reason to conclude that the drug caused the event.

### **8.1.3 Suspected adverse reaction**

A suspected adverse reaction is defined as any adverse event for which there is a reasonable possibility that the drug caused the adverse event. For the purposes of IND safety reporting, “reasonable possibility” indicates that there is evidence to suggest a causal relationship between the drug and the adverse event. A suspected adverse reaction implies a lesser degree of certainty about causality than an adverse reaction.

